 - 4.8 Method of study
 - 4.9 Study closure
 - 4.10 Documentation and communication
- 5. Study Outcome Measures
 - 5.1 Primary outcome measures
 - 5.2 Secondary outcome measures
- 6. Study Population and Sample size
 - 6.1 Statistics and data analysis
- 7. Study supervision and monitoring
- 8. Regulatory issues
 - 8.1 Ethics approval
 - 8.2 Consent
 - 8.3 Confidentiality
 - 8.4 Indemnity
 - 8.5 Sponsor
 - 8.6 Adverse events
 - 8.7 Audits and inspections
- 9. Study management
- 10. Publication policy
- 11. References

12. Appendix

- 12.1 Flow chart outlining patient pathway and summary of investigations
- 12.2 Consent forms
- 12.3 Patient information sheets

1. Study Summary

Title

Psychology of pregnancy of unknown location (SOUL)

Design

Prospective cohort observational study

Primary aim

To assess the psychological impact of pregnancy of unknown location (PUL) classification pending a final diagnosis.

Secondary aims

To assess psychological burden of PUL on patients and their partners. To assess if shortening time to providing patients classified with PUL with results and advice using point-of-care beta human chorionic gonadotrophin (BhCG) testing reduces psychological burden.

Hypothesis

- 1) PUL causes significant psychological distress to patients and their partners which can be assessed using a validated psychological tool.
- 2) Increasing the efficiency of PUL management will reduce anxiety and depression symptoms in patients and their partners.

Outcome measures

Psychological morbidity will be assessed using the HADS on time of PUL classification, 48 hours from PUL classification and following final diagnosis and management.

Eligibility

Pregnant women attending the Early Pregnancy Unit in the first trimester (up to 14 weeks gestation) with a pregnancy of unknown who are over 18 years old and are able to give consent.

Duration

The study will be conducted over a minimum period of two years.

Keywords

Pregnancy of unknown location, beta-human chorionic gonadotrophin, depression, anxiety.

2. Introduction

2.1 Background and study rationale

a. Pregnancy of unknown location and Ectopic pregnancy

Pregnancy of unknown location (PUL) is a syndrome of early pregnancy composed of a positive urine pregnancy test without the visualisation of a pregnancy on trans-vaginal ultrasound (TVUS). There are four possible final diagnoses from PUL: intrauterine pregnancy (IUP); failing pregnancy of unknown location (FPUL); persistent pregnancy of unknown location (PPUL); and ectopic pregnancy (EP) [1].

The initial investigation that is currently performed with TVUS is serum beta human chorionic gonadotrophin (BhCG) testing. Previous studies however have highlighted that the traditional single serum hCG testing following TVUS is a poor predictor of outcome, viability and location of PUL [3].

b. BhCG monitoring and modelling

hCG (a glycoprotein produced by syncytiotrophoblast cells responsible for maintaining the corpus luteum in early pregnancy). hCG is hetrodimeric and consists of an alpha and beta subunit. The beta subunit is unique to hCG and is therefore clinically useful in pregnancy. The use of beta hCG (BhCG) and progesterone levels in the management of PUL is commonplace [4-5]. However, interpretation of the results can be subjective [6-7].

A statistical logistical regression model which utilised initial BhCG levels and BhCG ratio (48hour BhCG divided by 0 hour BhCG) was created by a research group with the aim of allowing PUL to be safely risk stratified [8-14]. This has been validated and found to be superior to isolated progesterone and BhCG protocols, although unclear how applicable this may be to populations such as the United States [14-15]. A modified and validated model has since been trialled and used in a multi-centre study across North West London in order to optimise PUL risk stratification into 'low risk' (encompassing IUP and FPUL) and 'high risk' (encompassing PPUL and EP) [2]. This was part of the Assessment of Biomarkers and Ultrasound in Pregnancy of Unknown Location and Ectopic Pregnancy study (ABPEP) which utilised serial BhCG observation (at 0 hours and 48 hours from diagnosis of PUL), BhCG ratio along with progesterone testing [2].

This model has come to be known as the 'M6 model' and was developed from a cohort of 2753 cases of PUL. It classified 62.1% PUL as 'low risk' with a negative predictive value of 98.6% [2]. This the model which we currently adopt in our unit.

SOUL, VERSION 5

September 2021

c. Point of care BhCG testing

BhCG measurements require serum samples sent to hospital laboratories in order to assess levels in a standardised manner. However, point of care (POC) BhCG testing is now available that uses whole blood to provide lab-quality, quantitative results in minutes. This could lead to a reduction in time waiting for results as well as a reduction in the associated psychological distress to patients and their partners [16]. The only food and drug agency approved quantitative test is the i-STAT BhCG (Abbott POC) test that could play a role in providing quick results that are comparable to hospital laboratory analysis. This could therefore be used to risk stratify within a risk prediction model [17]. The Abbott POC test is CE marked, confirm its conformity with European standards for health and safety of products sold within the European Economic area.

d. Anxiety and Depression related to Early Pregnancy Loss

Anxiety, depression and post-traumatic stress disorder (PTSD) are recognised complications following early pregnancy loss. A systematic review of 27 papers exploring the psychological impact of early pregnancy loss identified significant depression and anxiety within the first month, with 8-20% moderate depression and 18-32% anxiety reported at 4-6 weeks [18]. A Cochrane review of six studies involving 1001 women demonstrated no single beneficial method of managing the psychological impact of early pregnancy loss, but that counselling may be beneficial [19]

A UK study of 160 women demonstrated that uncertainty in diagnosis, rather than the negative or positive connotations of the diagnosis itself, was a greater contributing factor in women's feelings of anxiety and depression in relation to PUL [20]. Furthermore, a local pilot study demonstrated women experiencing both miscarriage and ectopic pregnancy fulfilled criteria for PTSD, with many suffering from moderate-to-severe anxiety and depression, with psychological morbidity persisting at least 3 months following pregnancy loss [21].

e. The Hospital and Anxiety Depression Scale

The Hospital Anxiety and Depression Scale is a 14-part questionnaire with 7 questions exploring symptoms of anxiety and depression respectively. Each question is answered with a scale of 0-3 to represent severity of symptoms, with an independent maximum score of 21 for depression or anxiety. A score \geq 11 is deemed moderate, whilst \geq 16 represents severe symptoms [22].

No single validated psychological tool is recommended for evaluation of these symptoms in the context of early pregnancy loss, and existing literature has relied on existing scoring

SOUL, VERSION 5

September 2021

systems, self-reported symptoms or structured interview [18, 19]. The HADS tool has been previously utilised in our unit for the psychological impact of early pregnancy loss in women experiencing miscarriage or ectopic pregnancy [21].

A 2002 review of 747 papers identified HADS has a Cronbach's alpha coefficient of 0.83 (0.68-0.93) for internal consistency of anxiety symptoms and 0.82 (0.67-0.90) for depression. It was found to perform well in symptom assessment in a range of clinical settings including in primary care, the general population and in somatic and psychiatric forms of depression and anxiety [23].

2.2 Study rationale and study hypothesis

a. Study rationale

PUL is a syndrome of early pregnancy composed of a positive urine pregnancy test without the visualisation of a pregnancy on trans-vaginal ultrasound (TVUS). The current method for risk stratifying a PUL is via serum BhCG levels at the time of identification of PUL and after 48 hours, in order to ascertain the viability of the pregnancy. Patients and their partners need to wait for this result before a management plan can be adopted, taking at least 2-3 hours.

There is a clear need for the patient care pathway to evolve in order to aid and improve the management of women classified with a PUL. By using point-of-care BhCG testing, we would shorten the time to management. We propose that shortening the time interval would reduce psychological morbidity.

b. Study hypothesis

- 1) PUL causes significant psychological distress to patients and their partners which can be assessed using a validated psychological tool.
- 2) Increasing the efficiency of PUL management will reduce anxiety and depression symptoms in patients and their partners.

3. Study Objectives

This study aims to improve the pathway of care to this cohort of women by:

- Assessing the psychological impact of pregnancy of unknown location (PUL) classification pending a final diagnosis.
- Assessing psychological burden of PUL on patients and their partners.

· Assessing if shortening time to providing patients classified with PUL with results and advice using point-of-care beta human chorionic gonadotrophin (BhCG) testing reduces psychological burden.

4. Methodology and Design

4.1 Study centre

The primary centre for the study will be Queen Charlotte's and Chelsea Hospital, part of Imperial Healthcare NHS Trust).

Secondary centres will include St Mary's Hospital (part of Imperial College Healthcare NHS Trust).

There will be:

- A named individual (clinical research fellow CRF) in the primary study centre who will be responsible for co-ordinating the project, reporting to the chief investigator and co-ordinating the study at the secondary study centres;
- Regular inspection by the named individual under the supervision of the chief investigator in order to ensure both the service (literature, communication, documentation, supervision and logistics) and facilities (ultrasound, equipment, space) are of a high standard;
- Assurances that those who contribute to the study are experienced and trained in the management of patients presenting to an Early Pregnancy Unit (e.g. specialist nurse, research nurse, sonographer, gynaecologist);
- A PhD thesis documenting the outcome.

4.2 Design and links to previous studies

a. Design

SOUL is prospective cohort observational study focussing on psychological assessment of patients and their partners with PUL.

b. Links to previous studies

Pilot study undertaken in the unit in 2016 by Farren J et al [21], led by Chief Investigator [name], explored the severity and type of emotional distress in women after early pregnancy loss compared with women with ongoing pregnancies (REC 11/SW/0052). This group implemented HADS.

4.3 Duration

The study will be conducted over a minimum of one year to ensure adequate recruitment and follow up.

4.4 Inclusion criteria

Pregnant women attending the Early Pregnancy Unit in the first trimester (up to 14 weeks gestation) with a pregnancy of unknown who are over 18 years old and are able to give consent.

4.5 Exclusion criteria

Presence diagnosed with cancer, the presence of an acute medical condition, patients/partners aged less than 18 years, patients or partners who cannot give fully informed study consent (language or learning impairment), presence of a viable intrauterine pregnancy, ectopic pregnancy and miscarriage.

4.6 Withdrawal criteria

Patients and/or their partners may withdraw from the study at any stage and all data captured in relation to their participation may be destroyed at their request.

4.7 Consent and information leaflet

Regarding written consent, participants will be given sufficient time to consider recruitment and consent to participate so long as they are clinically stable and that the time taken does not compromise safety and management.

Patients who wish to participate in the study will be provided with a patient information sheet and they will be given a minimum of 15 minutes without the research team present to consider whether they wish to participate. There will be separate patient information sheets for women and their partners. They will be made aware that participation is voluntary and that they can withdraw from the study at any point without affecting their usual care. They will have then have time to formulate and ask questions and time to discuss the study with a relative or personal doctor. If the patient or partner wishes to enter the study, this will be documented on the ultrasound scan notes and the consent form will be completed.

Three copies will be taken, one to the participant, one with health records, one kept by the Chief Investigator within the study file. Good Clinical Practice (GCP) training is mandatory for training in consent for research purposes.

4.8 Recruitment Process

The recruitment process will be undertaken within EPU. The participants could potentially be any woman who is referred or who presents to the early pregnancy assessment unit (EPAU) and requires a trans-vaginal ultrasound scan and will be identified by a member of the clinical care team on EPAU who is scanning, who has signed the delegation log and who is certified with Good Clinical Practice (GCP).

Those that will be invited to participate in the study will include patients and their partners attending the Early Pregnancy Unit in the first trimester (up to 14 weeks gestation) classified with a PUL on trans-vaginal ultrasound scan over the age of 18.

All patients and partners will first be approached by members of the direct care team before being invited to the study once a PUL has been classified using TVUS. Members of the direct care team (if not part of the research team) will ask patients if they can them refer them to a member of the research team.

Advertising using posters in the EPU will be used in order for patients and partners to view the research being offered in the unit and any interest will be referred to the research team where they can ask questions and discuss the study further. The poster that will be on the walls of the early pregnancy unit (EPU) located on the second floor of Hammersmith Hospital, part of Imperial College Healthcare NHS Trust, [name]. Contact details on the poster will allow participants to contact the team through email or over the phone in order to ask questions. There will be separate posters for phases one and two of the study.

Written consent will be required for all aspects of the study. Participants will be made aware that participation is voluntary and that they can withdraw from the study at any point without giving any reason and without affecting their usual care.

Patients and partners will first be approached by members of the direct care team. If they are not part of the research team, they will refer the patient and partner to a member of the research team if the patient and partner give them verbal consent to do so. Patients and partners will then be seen by a member of the research team.

Patients and partners that approach through advertising will be referred to a member of the research team. This may be face to face, or via the contact details available on the poster. If

the patient meets the inclusion criteria, they will be invited to the EPU if not present in the unit already.

4.9 Method of study

This is a cohort study and will recruit patients in the first trimester (less than 14 weeks gestation) and their partners who meet the inclusion criteria attending the Early Pregnancy Unit. There will be two phases of the study, each with a minimum duration of 4 months. Phase 1 aims to establish the psychological burden of PUL under the existing care pathway, whilst phase 2 introduces point of care BhCG testing in clinical practice. The phases of the study are described in more detail below.

An information leaflet detailing the purpose of the study will be provided, and separate patient information sheets will be used for each phase of the study. A minimum of 15 minutes will be provided for patients to read the study information with the research team not present. Patients will then have opportunity to elicit further information or clarification from the research team. There are no significant ethical, legal or management issues. Women who both verbally consent and consent in writing will follow a well-defined pathway (see flowchart appendix).

The phases of the study are

- Group 1: Assessing the psychological impact of pregnancy of unknown location (PUL) classification pending a final diagnosis. Confirming the reliability of point of care testing in correlation with laboratory BhCG levels (gold standard).
- Group 2: To assess if shortening time to providing patients classified with PUL with results and advice using point-of-care beta human chorionic gonadotrophin (BhCG) testing reduces psychological burden.

Women with symptoms in the first trimester are routinely seen in the Early Pregnancy Unit (EPU). A clerking proforma is completed, urine is tested and a transvaginal ultrasound scan is performed. Blood testing and follow up arrangements are made if required with blood results inputted into a validated statistical model if a patient is classified with a PUL.

Participants in phase one of the study will not be provided with the POC BhCG result. They will await the laboratory result. Simultaneously we will ascertain reliability of POC in clinical practice during this time.

Patients in phase two will be provided with the POC test result, which will reduce the time to which they receive the result. Prior to transfer from phase 1 to phase 2 of research, correlation between POC and laboratory BhCG levels will be calculated in order to confirm its reliability by creating a correlation curve using the data.

Patients and partners will be asked to complete the questionnaire at three time points: 1) On classification of PUL at time zero once blood is taken, 2) at the 48-hour time point after blood is taken (if 48-hour bloods are required for the patient); and 3) after definitive diagnosis and management.

The maximum number of questionnaires that will be completed will be 6: 1 for each time point for the patient and 1 for each time point for the partner.

The questionnaires for the first two time points will be offered electronically whilst the patient is having their blood sample taken via use of a quick response matrix barcode (QR code). The third time point HADS will be texted through the encrypted system Accurx. We will contact the patient a maximum of 3 times to complete the questionnaire at the third time point to reduce loss of follow up.

The results will be submitted electronically each time. The results will be reviewed on a weekly-biweekly basis by the research team.

If patients score for moderate to severe anxiety or depression at any time point, we will call the patient. If they are struggling with their PUL classification or diagnosis, we will advise them to make an appointment to see their GP as soon as possible to arrange appropriate follow up, whilst clarifying any ongoing follow up at the early pregnancy unit. If patients score for moderate to severe anxiety or depression at any time point where no further follow up at the unit is indicated, we will also ask permission to send a text over Accurx that will list information relating to local miscarriage support groups, Tommy's Miscarriage charity, Petals Baby Loss Counselling Charity, the Ectopic Pregnancy Trust, the Miscarriage Association and Improving Access to Psychological Therapists (IAPT). If further support is required, they will be advised to contact their GP as soon as possible.

a. Symptoms

Patients will be asked to complete the standard clerking proforma used within the unit, including demographic data and information regarding previous obstetric, medical and gynaecological history and questions regarding symptoms.

b. Ultrasound

Trans-vaginal ultrasound is then performed as part of standard practice. Women with a PUL will be identified as eligible for the study

Any ultrasound abnormality detected will be managed in accordance with local and national guidance. Follow up trans-vaginal ultrasound for all will be arranged as per routine clinical practice if required.

c. Assessment of psychological symptoms

Patients diagnosed with PUL and their partners will be offered to take part in the study. Participants will be asked for written consent prior to point-of-care BhCG testing and completion of the HADS tool. The HADS tool takes 2-5 minutes to complete [22].

d. Clinical intervention

Performed in EPU as part of PUL classification:

- Transvaginal ultrasound
- 20ml venous blood sample

Performed in EPU or on the gynaecology ward following consent to participate in study:

- HADS tool
- 1ml sample of blood for point-of-care BhCG testing

e. Cataloguing

All data collection will be compliant with the Data Protection Act. The pseudonymised details will be logged onto a protected database with access restricted to only those personnel involved in the study. The data will be archived for secondary analysis.

Patients will be followed up for the duration of their care in the Early Pregnancy Unit. There will be no additional visits planned for research purposes.

Patients would remain in the study for a maximum of 2 months allowing time for final diagnosis and relevant follow up following intervention.

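### Phase 1 against phase 2 is a before-after contrast: the point-of-care aim is worded causally, and no analysis of the comparison is stated

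*Combined protocol and SAP*

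**What the plan says.** - **Design.** Section 4.2: "SOUL is prospective cohort observational study focussing on psychological assessment of patients and their partners with PUL". Section 4.9 (Method of study): "There will be two phases of the study, each with a minimum duration of 4 months". Phase 1 women wait for the laboratory result and are not given the POC result; phase 2 women are given it.
- **Order.** The POC and laboratory values are to be correlated "Prior to transfer from phase 1 to phase 2 of research" (section 4.9), so phase 2 follows phase 1. No randomisation or concurrent control is described.
- **Aim and hypothesis.** The secondary aim (section 1, repeated in section 3 and for Group 2 in section 4.9) asks whether "shortening time to providing patients classified with PUL with results and advice using point-of-care beta human chorionic gonadotrophin (BhCG) testing reduces psychological burden". Hypothesis 2 (sections 1 and 2.2) reads "Increasing the efficiency of PUL management will reduce anxiety and depression symptoms in patients and their partners".
- **Analysis.** Section 6.1 holds recruitment feasibility and sample sizes. For women it gives 62 per phase, from 32% against 10% with moderate to severe anxiety in the pilot's cases and controls. For partners it gives 47 per phase, from 30% of women against 6% of partners. Both use a type 1 error of 0.05 and 80% power. No test, model or effect measure is named for the phase comparison. Section 7(b) mentions interim and final analyses without content. The only analysis described is the POC/laboratory correlation.
- **Data available.** HADS anxiety and depression (each 0-21) are requested at time zero, at 48 hours if bloods are needed then, and after diagnosis and management.

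**The concern.** Each woman's exposure is fixed by when she attends. Anything else that differs between the two periods enters the comparison on the same footing as POC testing. Case mix is one candidate, since section 2.1 says "There are four possible final diagnoses from PUL". Background anxiety and partner attendance are others. Participants also know which phase they are in, because "separate patient information sheets will be used for each phase of the study" (section 4.9).

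The intended gain is a shorter wait. Section 2.2 describes the current one: "Patients and their partners need to wait for this result before a management plan can be adopted, taking at least 2-3 hours". A conclusion that shortening this wait reduced distress would need the two periods to be otherwise alike, which this design cannot show.

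With no analysis stated, the only guide is the sizing contrast: unadjusted, dichotomised and on anxiety alone, while hypothesis 2 also covers depression. If that contrast became the analysis, a period difference would be credited to POC testing, and the full scores and time-zero values already requested would not contribute to the comparison.

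**Working it through.** **1. The plan's own figure.** Inputs from section 6.1: p1 = 0.32, p2 = 0.10, alpha 0.05 (taken as two-sided), power 80%, ratio 1:1.

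n = [1.960 √(2 × 0.21 × 0.79) + 0.842 √(0.32 × 0.68 + 0.10 × 0.90)]² / 0.22² = (1.129 + 0.467)² / 0.0484 = 52.6

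With continuity correction: (52.6 / 4) × [1 + √(1 + 4 / (52.6 × 0.22))]² = 61.4, so 62. The same steps for 30% against 6% give 39.0, then 47.0, so 47. Both stated sizes reproduce. The rates behind them are cases against controls and women against partners, not phase 1 against phase 2.

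**2. What a background change does to the sizing contrast.** Assume 32% in phase 1, no POC effect and 62 per phase. Exact binomial enumeration of the chi-square test gives:

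| Phase 2 rate | Significant, uncorrected | Significant, corrected |
|---|---|---|
| 32% | 4.9% | 3.2% |
| 27% | 9.3% | 6.5% |
| 22% | 24.0% | 18.5% |
| 17% | 49.4% | 41.7% |

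The size of the fall is assumed; the documents give none.

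**3. Power for a real effect.** Assumptions: a 2-point reduction in anxiety score, SD 4.5, correlation r with time-zero HADS of 0.4-0.6, 62 per phase, complete follow-up.

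- *Cut-off.* If 32% score 11 or more in phase 1, the mean is 10.5 − 4.5 × 0.468 = 8.4. After a 2-point fall, (10.5 − 6.4) / 4.5 = 0.91, so about 18% score 11 or more. Power for 32% against 18% is about 43-44%.
- *Unadjusted score.* SE = 4.5 × √(2/62) = 0.808; 2 / 0.808 = 2.47; Φ(2.47 − 1.96) = 70%. Simulation with rounded scores held within 0-21 gives about 69%.
- *Baseline-adjusted score.* The SE is multiplied by √(1 − r²), giving 0.741, 0.700 and 0.647 for r = 0.4, 0.5 and 0.6. Power is Φ(0.74) = 77%, Φ(0.90) = 82% and Φ(1.13) = 87%; simulation gives about 75-86%.

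The step from cut-off to score is worth about 25 points (69 − 44). At r = 0.4-0.5 most of the gain therefore comes from using the score, not from the adjustment. If 20% of third forms are missing (50 per phase), simulated power is 65-77% adjusted against 35-37% for the cut-off.

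**4. The same model under a background change.** Assume no POC effect and a shift equal to 32% falling to 22%; at SD 4.5 this is 4.5 × (0.772 − 0.468) = 1.37 points. Simulated chance of a significant result, 62 per phase:

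| When the shift arises | Cut-off | Adjusted score |
|---|---|---|
| Already present at time zero | about 24% | about 13-20% |
| Only after time zero | about 23-25% | about 43-55% |

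With no shift, the adjusted model rejects about 5% of the time. Comparing time-zero HADS between phases detects the first kind of shift only 38-40% of the time and cannot see the second.

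**The case against.** The protocol is open about its design: it calls itself an observational cohort, says the study will initially be a pilot, and gives a reason for the order of the phases. A directional hypothesis is common in such protocols, and no causal conclusion has yet been drawn. That stands, and it limits the weight of the point. It does not remove the mismatch between the causal wording and what sequential cohorts can show.

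A reader might infer that the plan has chosen an unadjusted comparison of proportions. The documents do not say so: section 6.1 sizes the study that way and is silent on the analysis. The fault is the silence.

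A reader might also infer that the pandemic made the phases differ. The second section numbered 4.9 (Study closure) says only that partners cannot attend and that patient recruitment is under way. The restriction may cover both phases, and no difference in case mix or anxiety is recorded. Period confounding is a feature of the design here, not an observed fact.

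Finally, the adjusted model could look like the cure. It is not: under a shift arising after time zero it is falsely significant about twice as often as the cut-off.

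**Conclusion.** The point holds in a limited form. The phase comparison is before-after, POC testing and calendar period cannot be separated, the aim and hypothesis 2 are worded causally, and no analysis is stated. The sample-size arithmetic is correct.

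Under the stated assumptions, using the full score with baseline adjustment raises power from about 43-44% to about 75-86%. That is a gain in precision only. False significance under a shift equal to 32% to 22% ranges from about 13-20% to about 43-55%, depending on when the shift arises. Effect, SD, correlation, loss and shift are all assumed, not taken from the documents. The power figures for 62 per phase cannot be carried to the 48-hour form, which only women needing 48-hour bloods complete.

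This should be changed, and no stronger rating is justified: it concerns a secondary aim of a self-described pilot.

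**What to change.** 1. Word hypothesis 2 and the eventual conclusion as a before-after association, and state that period effects cannot be excluded. This is the real protection.
2. Compare the phases on the 0-21 HADS score, for anxiety and depression separately, with a linear model adjusted for time-zero HADS. Report the adjusted difference with its 95% CI beside the proportion scoring 11 or more.

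The cost is wording and a little analysis on data already requested; the order of the phases need not change. Three limits belong beside the model. It only partly removes a shift already present at time zero. It does not remove a later shift, and is then more often falsely significant than the cut-off. And if the phase-specific information sheets move time-zero scores, adjustment could take out part of a real difference.

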4.9 Study closure

We aimed to recruit approximately 250 participants in total (at least 62 patients and 47 partners per phase) with a minimum study duration of two years. The end of the study will be following the analysis of the patients' questionnaires.

However, in light of the SARS-CoV-2 pandemic, partners cannot attend early pregnancy units. It is likely that data from patients only will be possible to be collected as we will not be able to make up the difference regarding partners as patient recruitment is already under way. The total we will be able to recruit will therefore be at least 124 (at least 62 patients per phase). Although this reduces the scope of the study, we will still be able to meet the vast majority of our objectives.

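### The pre-phase 2 check of point-of-care BhCG rests on correlation, which cannot show constant or proportional bias, and no acceptance limit is set

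*Combined protocol and SAP*

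**What the plan says.** Section 4.9 (Method of study) gives phase 1 two tasks. One is psychological. The other is described as "Confirming the reliability of point of care testing in correlation with laboratory BhCG levels (gold standard"). During phase 1 patients wait for the laboratory result and are not told the POC result. The check has a fixed place in the sequence, "Prior to transfer from phase 1 to phase 2 of research", and a named method: "correlation between POC and laboratory BhCG levels will be calculated in order to confirm its reliability by creating a correlation curve using the data". After that, "Patients in phase two will be provided with the POC test result".

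The paired data come from routine laboratory blood and a "1ml sample of blood for point-of-care BhCG testing" (section 4.9, Clinical intervention).

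Section 6.1, where the statistics are set out, does not mention the comparison of POC with the laboratory. No target correlation, maximum bias, limits of agreement or consequence of failure appears anywhere in the text available. Section 2.1(c) describes the device as CE marked and comparable to laboratory analysis, but quotes no bias or imprecision figure.

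**The concern.** The stated purpose is to confirm that POC readings can be relied on in place of the laboratory's. That is a question of agreement: how far, and in which direction, does POC differ from the laboratory on the same sample? A correlation coefficient answers a different question. It is unchanged if every POC value is multiplied by a positive constant or shifted by a constant. It also stays high under sizeable random error when values are widely spread, as BhCG values are likely to be. Followed as written, the plan could declare a biased device reliable, and it contains no result that would count as failure.

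What is at stake is the claim of reliability against the gold standard, made just before patients start to receive POC results. Consequences for risk classification are conditional. Section 2.1(b) describes a model family that uses the initial BhCG level and the ratio of the 48-hour to the 0-hour level. Section 2.1(c) says of POC testing that "This could therefore be used to risk stratify within a risk prediction model". Section 4.9 says that blood results go into a validated model, without saying whether POC results are among them. If they are, bias would affect the initial level. Random error, an additive offset, or a mixture of POC and laboratory readings would affect the ratio. A constant proportional bias cancels when both readings are POC.

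**Working it through.** The plan gives no figure for this comparison, so there is none to reproduce. The 62 women per phase come from section 6.1, where they are sized on anxiety rates (32% v 10%); 62 is used below only as the likely number of phase 1 pairs.

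**Step 1: algebra, no assumptions.** For any a and any k > 0, corr(lab, a + k × POC) = corr(lab, POC). So r carries no information on an offset a or a proportional bias k.

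**Step 2: illustration.** The documents give no BhCG spread, device CV or bias. Assumed: laboratory values log-normal with median 400 IU/L and log-SD 1.3 (range 1.0 to 1.6); POC = k × lab × exp(e), where e is normal with mean 0 and SD equal to the CV; 62 pairs; 20,000 replicates.

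Mean r by random error:

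| CV | log-SD 1.3 | log-SD 1.0 to 1.6 |
|---|---|---|
| 5% | 0.9987 | 0.998 to 0.999 |
| 10% | 0.995 | 0.993 to 0.996 |
| 15% | 0.988 | 0.984 to 0.991 |
| 20% | 0.979 | 0.971 to 0.984 |

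So r stays above 0.97 on average even at 20% random error.

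Effect of bias at 10% CV and log-SD 1.3, same draws throughout:

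| Device | Mean r | Geometric mean POC/lab | Limits of agreement, factor either side |
|---|---|---|---|
| Unbiased | 0.995 | 1.00 | 1.22 |
| × 0.8 | 0.995 | 0.80 | 1.22 |
| × 0.7 | 0.995 | 0.70 | 1.22 |
| × 0.5 | 0.995 | 0.50 | 1.22 |
| × 1.3 | 0.995 | 1.30 | 1.22 |
| + 100 IU/L | 0.995 | about 1.43 | about 2.1 |

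**Step 3: what an agreement analysis of 62 pairs would deliver (CV 10%).**

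- 95% CI for bias: exp(t × CV/√62) = exp(2.00 × 0.10/7.87) = a factor of 1.026 either way. For a device reading 30% low: 0.70/1.026 = 0.68 and 0.70 × 1.026 = 0.72, that is, -32% to -28%.
- Limits of agreement: exp(1.96 × 0.10) = a factor of 1.22 either side of the bias.
- Uncertainty of each limit: about 0.43 to 0.44 SD, a factor of about 1.045.

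**Step 4: the ratio, only if POC values form it.**

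- Random error: 95% factor exp(1.96 × √2 × CV) = 1.15, 1.32, 1.52 and 1.74 at CV 5%, 10%, 15% and 20%.
- Offset of +100: a rise from 200 to 330 has ratio 1.65; with the offset it is 430/300 = 1.43.
- Mixed methods with × 1.3 bias, POC at 0 hours and laboratory at 48 hours: 330/(1.3 × 200) = 1.27 instead of 1.65.
- × 1.3 on both readings: cancels, ratio 1.65.

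**The case against.** - **A correlation curve may be more than a coefficient.** If it means a scatter plot with a fitted line, bias could be seen. Under the assumptions above, a device reading 30% low gives a mean fitted slope of 0.70 (95% range 0.62 to 0.79). That is fair, but the term is undefined, and the plan does not say that a slope or intercept will be estimated or judged against anything.
- **Log-scale Bland-Altman represents an additive offset poorly.** True in part: the +100 case appears as a ratio of about 1.43 with limits widened to a factor of about 2.1, so some of the offset looks like scatter. The analysis still flags the device, and regression separates the two components.
- **The device is CE marked and described as agency-approved, and an analytical evaluation is cited.** That source may hold bias figures; they are not in the protocol. The plan itself chose to confirm reliability locally, and external approval does not turn correlation into a test of agreement.
- **The check is ancillary.** POC reliability is not among the objectives in section 3 or the outcomes in section 5, and HADS is unaffected. This stands, and it limits the severity. Phase 2 safeguards might also sit in the flow chart, which is not available here. Even so, the check is a named phase 1 task placed before patients receive POC results.

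**Conclusion.** The concern holds and should be fixed. The only named analysis cannot do what it is meant to do, and no outcome of it would stop phase 2. That r is blind to offset and proportional bias is exact and needs no assumption. The sizes (mean r of 0.995 at 10% error whatever the bias, against a bias estimated to within a factor of 1.026) rest on the assumed log-normal spread, error and 62 pairs. Nothing here shows that the device is biased, and the HADS comparison between phases is not invalidated by this point. Effects on risk classification depend on whether POC values enter the model, which the documents leave open.

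**What to change.** 1. Replace the correlation criterion in section 4.9 with an agreement analysis of the paired phase 1 samples: log-scale Bland-Altman, giving mean percentage bias and 95% limits of agreement, each with a confidence interval. Deming or Passing-Bablok slope and intercept are a useful addition, because they separate an offset from a proportional bias.
2. State whether POC values will enter the risk model. If so, and where 48-hour POC/laboratory pairs exist, add agreement of the 48-hour/0-hour ratio and of the model risk class.
3. Have the unit's clinical and laboratory leads set acceptance limits before the paired data are analysed, and make the start of phase 2 conditional on meeting them.

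The cost is protocol wording and one further analysis of samples already planned, with no new blood draw. The Study closure section says "patient recruitment is already under way", so the limits can no longer precede collection, but they can precede analysis if the pairs have not yet been examined; if they have, the protocol should say so. The downsides are that phase 2 may be delayed if the limits are not met, and that the ratio analysis may have few pairs or none: the 48-hour time point applies only "if 48-hour bloods are required for the patient", and a 48-hour POC test is not stated.
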